6.0 Enrollment/Randomization

Following baseline assessments, patient-caregiver dyads ($N = 50$) will be randomly assigned to the ACT intervention or education/support condition in a 1:1 ratio using a stratified block randomization scheme to balance the groups by patient performance status (Eastern Cooperative Oncology Group scores 0 or 1 vs. 2).^{48, 50} We will stratify randomization by performance status because the decision to provide chemotherapy and other cancer treatments is often based on performance status.⁵¹ Randomization will be performed using a SAS procedure routinely employed by the IU Biostatistics Department. The study statistician will create the randomization procedure, and the PI will inform study therapists of their assigned patients. Other members of the study team will remain blind to participants' group assignment. All patients will be registered with the Indiana University Cancer Center Clinical Trials Office. Applicable regulatory documents must be completed and on file prior to registration of any patients.

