Tertiary outcomes. Patients and caregivers will report their physical and mental healthcare use in five domains (e.g., ER visits, outpatient visits) in the past 3 months at baseline and over the study period.^{59, 60} These reports of healthcare use were sensitive to change in an R01-funded cancer trial.⁶¹ At all time points, participants will also report whether professionals referred them to support services and whether referred services were received.^{52, 62} At all time points, participants will also report current medications using established methods from prior trials.^{63, 64} We will compute the total number of medications at each time point, as this variable had strong predictive validity for both healthcare use and costs in older adults over a 1-year period.⁶⁵

Measures of symptom severity. Symptom severity will be assessed to characterize the sample. For both patients and caregivers, fatigue severity and frequency will be measured with six items from the FSI,^{36, 37} and sleep disturbance, cognitive symptoms, anxiety, and depressive symptoms will each be assessed with an 6-item PROMIS measure.^{40, 41, 49, 57, 58, 66} Patients will also complete 3-item and 4-item PROMIS measures of pain severity and impact on functioning, respectively.⁵⁸

ACT Intervention Procedures

Drs. [name] and [name] developed the ACT manual (see Table 3 and Appendix K), which was informed by literature on the experiences of advanced GI cancer patients and caregivers,^{2, 3, 15, 67, 68} the ACT model,^{24, 35} previous ACT trials with cancer patients and other populations with physical and mental health conditions,^{25, 26, 29, 31, 33, 34} and [name] extensive experience delivering ACT to cancer patients and caregivers. A licensed therapist will deliver the intervention. While the therapist will aim to hold sessions on a weekly basis for 6 weeks, participants will have up to 12 weeks to complete the 6 sessions. Patients and caregivers will complete sessions 1 and 4-6 together via speakerphone. Sessions 2 and 3 will be delivered to patients and caregivers separately. Holding both dyadic and individual sessions will allow the therapist to meet the shared and unique needs of patients and caregivers. We adapted ACT to the dyad by incorporating joint mindfulness practices and leveraging the relationship during discussions. For example, participants will discuss moments of emotional connection with each

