other as instances of mindfulness and provide encouragement to the other person during goal setting. Individual sessions with patients and caregivers will include exploration of personal values. In addition, the workability of attempts to avoid fatigue (if a patient) or unwanted thoughts and feelings about caregiving (if a caregiver) will be discussed. Thus, the focus of individual sessions is shifting from avoidant responses to the pursuit of value-based action despite fatigue or perceived caregiving burden.

According to the ACT model, psychological flexibility is established through the practice of six skills.⁶⁹ Each session has a primary focus on one of the six psychological skills (see Table 3), although in-session exercises and home practice generally promote multiple skills simultaneously. During the first session, the patient's and caregiver's background and coping strategies will be discussed, and the concept of mindfulness will be introduced. Patients will complete a 3-item version of the FSI, and patients and caregivers will complete a 4-item standardized assessment of anxiety and depressive symptoms at the beginning of each session (see Appendix L).^{36, 49} Completion of this assessment will allow the therapist to monitor and respond to participants' fatigue and distress. Paper copies of the questionnaires will be provided to participants to facilitate survey completion. Across the six sessions, participants will practice various mindfulness exercises, clarify their values, and set specific goals aligned with their values. Sessions will also include discussion of patients' and caregivers' experiences coping with cancer. Each session will include assessing and recording participants' home practice of mindfulness, value-based action, and other skills and will end with a discussion of practice for the week ahead. Through skill practice, participants will learn new, adaptive ways to respond to unwanted internal experiences (e.g., fatigue, distress). Handouts summarizing the topics of each session (Appendix M) and a CD that our team developed to guide mindfulness practices will be mailed to participants along with a box of raisins for a mindful eating exercise. Participants will also have the option of receiving the mindfulness recordings via an emailed link from IU Box.

Table 3. Summary of ACT Intervention Manual	
Topic (targeted ACT model skill)	Session and Home Practice (HP) Content

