Session 5 (dyadic) Detaching from Internal Experiences (Self as Context)	
 • Practice mindfulness (3-step self-compassion practice) with therapist • Exercises to promote observing and detaching from fatigue and emotions about cancer or caregiving to cultivate a transcendent sense of self from which to observe and accept changing experience HP5: Goal setting; practice value-based goal; daily mindfulness practice (person's choice on CD)
Session 6 (dyadic) Taking Steps to Do What Matters to You (Committed Action)	
 • Practice mindfulness (brief body scan exercise) with therapist • Recap of skills and what patient and caregiver learned • Goal setting around expanding values-consistent behavior into future • Termination and next steps in the study HP6: Continue written goals

Education/Support Condition Procedures

Dyads in the education/support arm will be directed to resources for practical and health information and contact information for psychosocial services. Thus, this study tests whether

ACT is superior to supportive listening and education on medical center and community resources, consistent with common interventions in clinical settings. The duration of sessions and number and order of dyadic vs. individual sessions will be identical to the ACT condition. A similar comparator was used in our ACT pilot trial with metastatic breast cancer patients,³⁴ and similar comparison groups have been used in studies with primarily advanced cancer patient-caregiver dyads.^{71, 72} A licensed therapist will deliver the

education/support intervention. Table 4 provides a summary of the topics for each education/support session, and the manual is found in Appendix N. While the therapist will aim to hold sessions on a weekly basis for 6 weeks, participants will have up to 12 weeks to complete the 6 sessions.

Education/support participants will complete the same weekly fatigue and distress assessments as those in the ACT condition. Sessions will include an orientation to the patient's medical center and treatment team, education regarding common QoL concerns and symptoms experienced by cancer

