- Participants will be fully informed about the study during the informed consent process and instructed to decline to answer any question or to discuss any issues they find troubling. If the interviewer feels that the participant is becoming anxious or fearful over a question, the interviewer will move on to the next question and document the reasoning.
- We will provide a letter with the principal investigator's and research assistant's names and phone numbers and instructions to call with questions or concerns.
- If a participant expresses significant distress (e.g., suicidal ideation) at any point during the study, Drs. [name] or [name] (both clinical psychologists) will assess the participant and make an appropriate referral for clinical care if needed. In addition, for distressed patients, [name] or another study team member will contact the referring oncologist to inform them of the patient's high level of distress. Patients will also be encouraged to contact the healthcare team if they experience moderate to severe symptoms.

Suicidality Risk Protocol

If a participant expresses suicidal ideation, our research team will use an evidence-based algorithm that was developed in 4 earlier depression effectiveness trials in medical patients⁷⁴⁻⁷⁷ and was tested in two recent trials in general medical (SCAMP trial)⁷⁸ and cancer (INCPAD trial)⁶⁰ patients. Evidence supports the utility of this algorithm (Appendix Q).⁷⁹ By this algorithm, participants are classified as minimal, lower, or higher risk. Participants with higher risk of suicide according to this algorithm will be considered for emergency detention. The latter constitute <2% of participants enrolled in depression trials, and we have a protocol for expedited evaluation by a clinical psychologist for the rare participant in the higher risk group, also tested in the SCAMP and INCPAD trials. All research personnel will be trained by the PI in this protocol. Specifically, after asking follow-up questions (see Appendix Q), [name] or [name] (both clinical psychologists) will review the information the same day to determine the

appropriate course of action. If they believe that the participant is in immediate danger of harm, they will report it, potentially to authorities including the police. If the participant is not receiving mental health services, then they will be referred to mental health services at a location convenient to them.

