Aim 2. Given that this is a pilot study, our data analytic approach for Aim #2 will be to derive effect size estimates rather than test for statistical significance. A linear mixed-model repeated measures approach (SAS Proc-Mixed) will be used to examine ACT's effects on primary and secondary outcomes. For outcome measures that only patients or caregivers complete (e.g., patient fatigue interference or caregiver burden), models will include main effects of time (as categorical) and study group and the time-by-study group interaction. Treatment effects will be evidenced by the interaction between time and study group (i.e., group mean differences after the intervention but no such differences at baseline). Models will include random intercepts to account for nonindependence of individuals' scores across time. For outcomes reported by patients and caregivers (e.g., psychological flexibility), multilevel modeling for dyadic data will be used.^{83, 84} Models will include the main effects of time, study group, and social role (patient vs. caregiver) as well as all two and three-way interactions between these variables. The time x study group x role interaction will estimate the degree to which treatment effects are different for patients and caregivers. Dyadic models will include random intercepts for patients and caregivers, as well as the covariance between the intercepts to account for nonindependence across time and across partners.

Aim 3. To conduct data analyses for Aim #3, we will use logistic and Poisson regression models to explore the effects of ACT on patient and caregiver physical and mental health service use (e.g., number of patient ER visits, patient and caregiver use of counseling and/or psychiatric medication). Logistic and Poisson regression analyses are appropriate for binary and count outcome data, respectively. Analyses will examine study condition as a predictor of health service use over the entire study period, controlling for baseline service use. Support service referrals will be a covariate in analyses of mental health service use.

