Statistical power. Although our analyses focus on effect sizes rather than statistical significance, we calculated power for comparing primary outcomes (patient fatigue interference and caregiver burden) between study groups. With a sample size of 34 patients and 34 caregivers at 2 weeks post-intervention (assuming 15% attrition), we will have 80% power ($\rho=.05$, two-tailed) to detect a large intervention effect ($d=.99$) on either primary outcome in a linear mixed model.⁸⁵ ACT had large effects on distress and QoL outcomes in late-stage ovarian cancer patients ($d=.89-1.69$) compared to CBT³³ and a medium effect ($d=-.59$) on fatigue interference compared to education/support in metastatic breast cancer patients with moderate-severe baseline fatigue interference.³⁴

Missing data. All data will be assessed for missingness and multiple imputation with 50 imputed samples will be used.⁸⁶ We will also compare participants and those who decline participation or withdraw on demographic and medical factors using t-tests and Chi-square analyses. Further, we will carefully track study participation and try to understand the reasons for dropout and missing data wherever possible. Identifying potential dropout and missing data mechanisms will allow us to incorporate those factors as auxiliary variables for multiple imputation as well as full information maximum likelihood estimation method assuming Missing at Random in our future Phase II trial.

Potential covariates. T-tests and chi-square analyses will be performed to identify any group differences in potential baseline covariates (e.g., demographic and medical variables), and if there are differences these variables will be used as covariates.

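### Aim 3 adjusts mental health service use for support service referrals without limiting them to baseline, so post-randomisation referrals can enter the model

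*Combined protocol and SAP*

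**What the plan says.** Section 11.0 (Aim 3) plans logistic and Poisson regression for service use and sets out the model: "Analyses will examine study condition as a predictor of health service use over the entire study period, controlling for baseline service use". The next sentence adds a further covariate for one group of outcomes: "Support service referrals will be a covariate in analyses of mental health service use". In the first sentence the word baseline belongs to service use. The second sentence has no time qualifier.

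Other places bear on the timing:

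- Section 7.0 (Tertiary outcomes): "At all time points, participants will also report whether professionals referred them to support services and whether referred services were received". Referrals are therefore recorded at baseline and at both follow-ups.
- Section 6.0 places random assignment after the baseline interview ("Following baseline assessments, patient-caregiver dyads" are then allocated 1:1). Both follow-up referral reports are post-randomisation.
- Section 11.0 (Potential covariates): "T-tests and chi-square analyses will be performed to identify any group differences in potential baseline covariates", with adjustment for those that differ. This rule selects baseline variables by imbalance. The referral covariate is included whatever the balance, so the rule does not govern it.
- Section 2.3 states the target as the effects of ACT on service use. No section says that an effect net of referral is wanted.

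**The concern.** Two analysts could follow Aim 3 faithfully and fit different models, one with baseline referral and one with referral at any time. The first raises no problem. The second conditions on something that happens after randomisation.

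Referral is a plausible step towards use of counselling or psychiatric care, and it shares causes with use, distress being the obvious one. If follow-up referral differs by arm, adjusting for it does two things. It removes the part of the arm effect that runs through referral, and it makes the arms differ in distress within each referral stratum. The coefficient is then neither the total effect nor, in general, a clean direct effect.

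An arm difference is plausible but not shown. Where a participant shows significant distress, a study psychologist "will assess the participant and make an appropriate referral for clinical care if needed". That rule is the same in both arms, but ACT sets out to change how people respond to distress. In the session summaries only the comparator lists service contacts: "Dyads in the education/support arm will be directed to resources for practical and health information and contact information for psychosocial services".

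What is at stake is the estimate for mental health service use in an exploratory aim, and whatever is carried from it into the larger trial that this pilot is meant to inform.

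A secondary point concerns count outcomes such as ER visits. Aim 3 names Poisson regression with no allowance for overdispersion. If the counts are overdispersed and intervals are reported, those intervals will be too narrow.

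**Working it through.** The plan states no figure for Aim 3, so there is nothing to reproduce. The documents give no referral or use rates, and every input in steps 1 to 4 is an assumption, except the sample sizes in step 3.

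**1. Model and assumed inputs.** Binary arm, distress (D), referral (R) and use (Y), with exact cell probabilities and no simulation:

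- Distress prevalence 50% in both arms.
- Referral: odds ratio (OR) 4 for distress. Among the undistressed, 20%, 30% or 40% are referred.
- Use: logit P(Y) = logit(0.10) + ln(4)·D + ln(3)·R, with no direct arm term. A second set replaces ln(3) by 0, so that referral has no effect on use.

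Referral among the distressed is then 50.0%, 63.2% or 72.7%. Overall referral is (20.0 + 50.0)/2 = 35.0%, (30.0 + 63.2)/2 = 46.6% or (40.0 + 72.7)/2 = 56.4%. With the referral OR at 3, use is 10.0% (neither), 25.0% (referred only), 30.8% (distressed only) and 57.1% (both). This gives overall use of 28.5%, 31.0% and 33.0% at the three referral levels. With the referral OR at 1, use is 20.4% in both arms.

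**2. Unadjusted and adjusted OR, ACT against control.** Unadjusted: the ratio of the odds of use by arm. Adjusted: the arm coefficient from a weighted logistic fit on arm and referral, with distress unmeasured.

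| Referral, control / ACT | Total-effect OR (referral OR 3) | Adjusted OR | Adjusted OR when referral has no effect (true OR 1.00) |
|---|---|---|---|
| 35% / 35% | 1.00 | 1.00 | 1.00 |
| 47% / 35% | 0.89 | 1.05 | 1.05 |
| 56% / 35% | 0.81 | 1.10 | 1.10 |
| 35% / 47% | 1.13 | 0.95 | 0.95 |
| 35% / 56% | 1.24 | 0.91 | 0.91 |

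The largest shift is 1.100/0.809 = 1.36. At the smaller gap it is 1.053/0.888 = 1.19. With the referral OR at 3, adjustment does not stop at 1.00 but crosses it, because distress is shared. The last column shows that part alone.

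A separate check without a shared cause assumed ACT referral of 30%, control referral of 40% to 80%, a referral OR of 2 to 8, and 20% use if not referred. The total-effect OR ran from 0.93 to 0.38 while the adjusted OR stayed at 1.00.

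**3. Sampling error for comparison.** SE(log OR) = √[1/(n·p₁(1−p₁)) + 1/(n·p₀(1−p₀))], and the 95% interval spans exp(1.96·SE) either side. Two sizes are used because Section 11.0 gives 34 at follow-up, that is 17 per arm, while its 15% attrition from 50 gives 50 × 0.85/2 = 21.25, taken as 21.

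| Per arm | SE, referral OR 3 | Factor | SE, referral OR 1 | Factor |
|---|---|---|---|---|
| 21 | 0.67 to 0.68 | 3.7 to 3.8 | 0.77 | 4.5 |
| 17 | 0.75 to 0.76 | 4.3 to 4.4 | 0.85 | 5.3 |

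For the adjusted OR the factor is 4.1 to 4.8 (referral OR 3) and 4.5 to 5.6 (referral OR 1).

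**4. Poisson intervals.** If the variance is φ times the mean, a nominal 95% interval covers 1 − 2·P(Z > 1.96/√φ). At φ = 2 this is 1 − 2·P(Z > 1.386) = 0.834. At φ = 3 it is 1 − 2·P(Z > 1.132) = 0.742.

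**The case against.** The strongest reply is that this is an ambiguity and not an error. The preceding sentence adjusts for baseline use and the general covariate rule concerns baseline variables, so a baseline reading is natural, and that reading does no harm. Harm needs follow-up referrals to be used, to differ by arm, and to be related to use.

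The evidence for an arm difference is thin. The referral rule and the session distress assessments are the same in both arms. Being given a contact is not the same as being referred by a professional. The full manuals are not shown, so the absence of contacts from the ACT summary table proves little. All this stands, and it is why the point is conditional and of low severity. It does not settle the timing, because no section limits the covariate to baseline.

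The illustration has no anchor in the documents. The factor of 1.36 comes from the widest assumed gap and is not an expected bias. The illustration also omits baseline service use, which Aim 3 includes. Adding it under assumed associations moved one adjusted value from 1.10 to between 1.08 and 1.09, so the omission is minor. Sampling error exceeds the shift throughout, but unlike sampling error the shift does not shrink as the sample grows.

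On the counts, naming Poisson regression does not rule out a robust variance, overdispersion alone does not bias the rate ratio, and the plan focuses on effect sizes. That part therefore matters only if intervals are reported.

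**Conclusion.** The concern holds as a conditional one. As written, Aim 3 allows adjustment for a variable measured after randomisation. If that variable differs by arm, the reported coefficient is not the total effect of ACT on mental health service use. Neither the sign nor the size can be derived from the documents. Under the assumed inputs the shift ranges from none (equal referral) to a factor of 1.36, and it can reverse the direction of the estimate. In a trial of 50 dyads this is well inside sampling error.

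The effect is confined to mental health service use, a tertiary outcome in an exploratory aim. No feasibility criterion or primary outcome is touched. The change is worth making because it is nearly free, but it is not essential. Confidence is medium, since a baseline covariate may be what was meant. The Poisson point is secondary: coverage of about 83% to 74% if the variance is two to three times the mean.

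**What to change.** In Section 11.0 (Aim 3), define the referral covariate as referral status reported at the baseline, pre-randomisation assessment, or drop it. Report follow-up referrals by arm descriptively. If a model adjusted for follow-up referrals is wanted as well, label it as a mediation or direct-effect analysis and do not present it as the effect of ACT.

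For the count outcomes, specify a robust, quasi-Poisson or negative binomial variance. Add a log-time offset only if the follow-up items cover a variable period, and set it to the period actually covered.

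The cost is one sentence for the covariate and one for the count models. No new data are needed, since baseline referral is already collected.
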